- a. Patients must remain in the hospital or be admitted to an in-patient facility for monitoring until at least Day 8. Study assessments may be delayed or moved ahead of the window to accommodate unforeseen delays after permission from the Medical Monitor. All procedures and examinations should be performed before the administration of study drug, except as indicated.
- b. Physical examination will include a full physical examination at Screening and on Day 1 (prior to dosing) and targeted physical exams on other days; see Section 7.13.
- c. Vital sign assessments for Day 1 must occur prior to administering study drug. See Sections 5.5.4.1 and 7.14.
- d. ECG must be done within 7 days prior to Day 1. See Section 7.15.
- e. Clinical data to be collected include:
 - Clinical support measures (eg, oxygen requirement) and physical activity limitations, see Section 8.1.1.
 - WHO Clinical Progression Scale, see Section 8.1.2.

Laboratory Assessments and Biomarkers:

- f. Safety laboratory assessments are categorized in two groups depending on the purpose:
 - For local laboratory assessments collected in this study, see Appendix 1A.
 - For central laboratory assessments collected throughout the study, see Appendix 1B.
- g. Hematology, serum chemistry, and coagulation assessments should be drawn in the morning.
- h. Predose samples should be collected up to 3 hours before study drug administration.
- i. End of infusion samples should be collected within 30 minutes of the end of study drug infusion.
- j. If the patient is discharged from the in-patient facility prior to Day 6, a sample will be collected between Days 6 to 10, inclusive. If the patient is unable to return to the clinic, samples may be collected by research staff or designee at an alternate location.
- k. See Section 7.11.1.
- 1. See Section 5.10.
- m. All biomarker samples should be drawn in the morning. See Section 5.11 for additional details.
- n. Collect oropharyngeal and anterior nares or nasopharyngeal swabs according to the CDC guidelines (CDC 2020b).

Study Drug Administration:

- o. See Sections 5.5.1 and 5.5.2 for additional details.

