- p. Patients should receive IV fluid as tolerated on the day of dosing (Day 1) and continue with oral hydration as tolerated for the subsequent 3 days. In the event patients cannot adhere to the oral hydration guidelines, IV hydration should be administered as clinically indicated. If the patient is prematurely discharged from the in-patient facility before Day 4, contact the patient (by telephone or clinic visit) once between Days 2 to 4, inclusive, to remind the patient of the oral hydration guidelines and to assess for any symptomatology and compliance with the hydration guidelines. Site personnel must document the hydration and the results of the discussion. Additionally, advise patients who are discharged from the in-patient facility before Day 8:
 - To restrain from activities that may contribute to dehydration (including, but not limited to, strenuous activity, long hot showers, and saunas) from Days 1 to 8.
 - If experiencing orthostatic symptoms, the patient should contact site personnel and consider increasing oral hydration.

See Section 5.5.4.2 for additional details.

- q. See Section 5.5.3 for additional details.
- r. The Safety Follow-Up call should occur 30 days (± 7 days) after discharge from the hospital or in-patient facility. If the patient remains at the in-patient facility after Day 8, the Safety Follow-Up call should occur no later than 38 days (± 7 days) after Day 1, the day of study drug administration. See Section 5.7 for additional details.
- Samples will be collected 30 days (± 7 days) after hospital or in-patient facility discharge for immunogenicity, DNA/RNA sequencing, SARS-CoV-2 serology, immune cell profiling, and detection of SARS-CoV-2 nucleic acid. Note:
 - If the patient is unable to return to the clinic, samples may be collected by research staff or designee at an alternate location.
 - If the patient remains at the in-patient facility after Day 8, samples should be collected no later than 38 days (± 7 days) after Day 1, the day of study drug administration.

See Section 5.7 for additional details.

t. If the patient is prematurely discharged from the in-patient facility, site personnel should contact the patient by telephone each day until Day 8 for collection of AEs and concomitant medications.

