2.2.3 Duration of Treatment for Study Drug (Bempegaldesleukin or Placebo)

Study drug administration will be limited to a single dose administration and monitoring in the hospital or in-patient facility will occur for a minimum of 8 days (ie, from Day 1 [day of dosing] to at least Day 8).

Patients will receive study drug in a hospital or in-patient facility setting.

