5.13 Adverse Events

All AEs, either reported by the patient or observed by study staff, will be reported from the time of first study drug(s) administration until 30 days after the last dose of study drug as described in Section 7.2.

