7.2 Monitoring AEs

All AEs will be assessed by the Investigator and recorded, including but not limited to, the following: the event term, the date of onset and resolution, seriousness, severity, relationship to study drug(s), outcome, treatment of the event, and action taken with the study drug(s). AEs will be reported starting immediately after the patient has been administered the first dose of study drug(s) until 30 days following the last dose of study drug(s).

An event occurring after the patient has provided informed consent, but before the first dose of study treatment, will be collected as medical history unless the event is either new and attributed to protocol-mandated procedures by the Investigator or there is a significant change in the rate of occurrence or an increase in the severity of the pre-existing condition which is judged to be clinically important and attributed to the protocol-mandated procedures by the Investigator. Under the latter 2 circumstances, the event will be considered an AE and will be captured as such.

• Example 1: Thrombophlebitis associated with a blood draw for assessments required prior to dosing per protocol is an event that is related to protocol-mandated procedures. In this scenario, the event of "thrombophlebitis" will be captured as an AE, and it will be documented as being "unrelated" to study drug(s), as applicable.

• Example 2: An ankle sprain following an unexpected fall from a flight of stairs while at home, after the patient has provided informed consent, but before the first dose of study drug(s), is clearly unrelated to any protocol-mandated procedures and would therefore be captured as medical history.

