7.5 AE Reporting and Follow-up

After initiation of study drug treatment, all AEs will be reported from the time of first study drug(s) administration until 30 days of last dose of study drug(s). For SAEs, additional reporting requirements also apply (see Section 7.7).

All ongoing AEs will be followed until resolution, the patient is lost to follow-up, patient death, or until the Safety Follow-Up call, whichever is earlier. In case the AE has not completely resolved by the Safety Follow-Up call, the final outcome of these ongoing AEs that are not related to study drug will be captured as "Not Recovered/Not Resolved" or "Recovering/Resolving", whichever is applicable. Any ongoing AEs at the Safety Follow-up call that are considered related to study drug will be followed until the event is resolved (with or without sequelae) or deemed stable. Any new AEs occurring after the Safety Follow-Up call will not be captured unless related to a study drug.

For specific instructions on identifying and reporting SAEs, see Sections 7.6 and 7.7.

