5.1 Definition of Common Variables

- Reference date (Day 1) = first dose date of study medication. If a patient has not been treated, the reference day will be set as missing.
- Study Day = assessment date reference date + 1 for assessments performed on or after the reference date or assessment date reference date for assessments performed before the reference date.
- Baseline: Baseline will be defined as the last non-missing value on or before the date of administration of the first dose of study medication (and time if available) unless it is identifiable by time that the value is after the first dose. For patients who have been not treated with any dose, then the baseline is defined as the screening value.

Time on study will be calculated as follows:

For visits/assessments/medications/therapies on or post study drug:

- Study hour will be calculated as follows:
- Study Hour = (assessment date time date time of the start of the first study dose)/60
- Study Day = (assessment date date of the first study dose) + 1, if assessment date is on or after the study dose date in that cohort
- Study Day = (assessment date date of the first study dose), if assessment date is prior to the study dose date in that cohort

For visit window derivation purpose, Study Day will be derived as ceiling of (Study Hour)/24.

For purposes of analysis and data display (i.e., means over time), actual visit hours/days are mapped to the planned study visit (i.e., nominal visits such as Hour 1, 2, Day 2, etc.) using visit windows. Acceptable visit windows around each scheduled procedure visit will be given for each measurement in the forthcoming sections. Due to the different data collection schedules for the various measurements, however, visit windows for different parameters might not be identical.

Unless otherwise specified, in mean and mean change from baseline/pre-dose summaries or analyses, if more than one value is obtained for the same measure within a given visit window,

the value closest to the planned study visit day and/or time will be used for reporting and analysis. If multiple values are equally away from the nominal visit day and/or time, the latter one will be used. However, for shift tables, the worst value mapped to that visit window will be used for summary purposes.

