11.2 Adverse Events

An AE is defined as any untoward medical occurrence in a subject who is administered a medicinal product and that does not necessarily have a causal relationship to the treatment. All AEs will be included in the data listings. Verbatim terms on case report forms will be mapped to preferred terms and system organ classes (SOC) using the Medical Dictionary for Regulatory Activities (MedDRA) (version 20.0).

A Treatment-Emergent Adverse Event (TEAE) is defined as an adverse event that occurs on or after the treatment dose, and treatment-emergent period is from the study dose date to 30 days after the study dose. The TEAE summary will be displayed by treatment using treatment-emergent period. Unless otherwise specified, summaries that are displayed by SOC and preferred terms will be ordered alphabetically by SOC, and within each SOC, preferred terms will also be ordered alphabetically. Summaries of the following types will be presented:

- TEAEs by MedDRA SOC and preferred term.
- TEAEs by MedDRA SOC, preferred term, and worst CTCAE grade (version 5.0). At each level of subject summarization, a subject is classified according to the worst CTCAE grade if the subject reported one or more CTCAE grade.
- TEAEs related to study drug by MedDRA SOC, preferred term, and worst CTCAE grade.
- TEAEs by descending incidence of preferred terms.
- Serious TEAEs by MedDRA SOC, preferred term and worst CTCAE grade.
- Serious TEAEs related to study drug by MedDRA SOC, preferred term, and worst CTCAE grade.
- TEAEs leading to early termination by MedDRA SOC, preferred term, and worst CTCAE grade.
- Any Grade \geq 3 drug-related AE.
- Respiratory compromise or other virus-related AE attributed to worsening COVID-19, such as severe hypoxia, cyanosis, or chest pain/pressure.
- TEAEs leading to deaths.

For each subject and for each adverse event, the duration of the event (days) will be calculated as:

Duration of AE (Days) = AE stop date - AE start date +1.

The duration of AEs will be displayed in the data listing.

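### For patients discharged before Day 8, the Safety Follow-Up call window opens before the 30-day AE period ends, so non-serious AEs judged unrelated can be missed

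*Protocol*

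**What the plan says.** **AE period, counted from dosing.** Protocol Section 5.13 has all AEs reported "until 30 days after the last dose of study drug as described in Section 7.2". Sections 7.2 and 7.5 give the same limit. Section 7.7 applies it to SAEs of any causality. SAP Section 11.2 uses the same window for analysis: "treatment-emergent period is from the study dose date to 30 days after the study dose".

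**Closing call, counted from discharge.** Footnote r to the Schedule of Events (Protocol Section 1.2) reads "The Safety Follow-Up call should occur 30 days (± 7 days) after discharge from the hospital or in-patient facility", and Section 5.7 repeats it. For patients who stay beyond Day 8, both places add a latest time of 38 (± 7) days after Day 1. Neither gives an earliest time relative to dosing.

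**What the call closes.** Protocol Section 7.5: "Any new AEs occurring after the Safety Follow-Up call will not be captured unless related to a study drug".

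**Length of stay.** Footnote a to the Schedule of Events: "Patients must remain in the hospital or be admitted to an in-patient facility for monitoring until at least Day 8". The protocol nevertheless plans for earlier discharge in footnotes j, p and t and in Sections 5.5 and 5.5.4.2. Section 5.8 treats such a patient as completing the study, with follow-up still timed from discharge. Daily AE telephone contacts after premature discharge stop at Day 8 (footnote t, Section 5.5).

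**The concern.** The two clocks agree only if the patient stays at least to Day 8. If the patient leaves sooner, the call moves earlier with the discharge date while the end of the AE period stays fixed. A site can then make the call within its permitted window, stop collecting new unrelated AEs as Section 7.5 says, and not deliver the period that Sections 5.13 and 7.2 promise and the SAP tabulates. The text adds a dose-based limit for long stays and none for short ones.

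AE incidence is a secondary objective that compares the arms (Protocol Section 3.2, SAP Section 2.2). SAP Section 11.2 applies one treatment-emergent window to everyone and does not allow for shorter observation. The percentages would then rest on unequal observation between patients. Discharge date is fixed after randomisation, so an equal effect in both arms cannot be taken for granted.

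**Working it through.** **Inputs**
- Dosing day is Study Day 1 (SAP Section 5.1: "Reference date (Day 1) = first dose date of study medication"). There is one dose (Protocol Section 2.2.3: "Study drug administration will be limited to a single dose administration"), so the first and last dose coincide.
- AE period: 30 days after that dose (Protocol Sections 5.13, 7.2 and 7.5; SAP Section 11.2).
- Call: 30 ± 7 days after discharge on Study Day d (Protocol Section 1.2 footnote r, Section 5.7).

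**The plan's own figure.** The limit of 38 days after Day 1 applies to stays beyond Day 8. The first such discharge is on Day 9: 9 + 30 = Study Day 39, and 39 - 1 = 38 days after Day 1. The figure is reproduced. With its tolerance the earliest time is 38 - 7 = 31 days after Day 1, which is Study Day 32, so long stays are covered.

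**End of the AE period.** 1 + 30 = Study Day 31.

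**Call window.** Earliest = d + 30 - 7 = d + 23. Nominal = d + 30. Latest = d + 37. The window holds 15 calendar days.

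**Shortfall at the earliest call.** 31 - (d + 23) = 8 - d, which is positive only for d < 8.

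| Discharge day d | Earliest call | Nominal call | Latest call | Largest shortfall (days) |
|---|---|---|---|---|
| 1 | 24 | 31 | 38 | 7 |
| 2 | 25 | 32 | 39 | 6 |
| 3 | 26 | 33 | 40 | 5 |
| 4 | 27 | 34 | 41 | 4 |
| 5 | 28 | 35 | 42 | 3 |
| 6 | 29 | 36 | 43 | 2 |
| 7 | 30 | 37 | 44 | 1 |
| 8 | 31 | 38 | 45 | 0 |
| 9 | 32 | 39 | 46 | 0 |

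Example, d = 2: a call on Day 25 leaves Days 26 to 31 after it. That is 6 days, and 6/30 = 20% of the AE period. Of the 15 permitted call dates (Days 25 to 39), 6 (Days 25 to 30) precede Day 31.

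**Nominal time.** d + 30 is at least 31 for every d from 1 upwards. The shortfall therefore arises only in the early part of the tolerance.

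**Sensitivity to the day count.** If Day 1 were counted as the first of the 30 days, the period would end on Day 30, the shortfall would be 7 - d, and the cut-off would be discharge before Day 7. The SAP's definition of Day 1 and the wording of the period as days after the dose favour Day 31.

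**The case against.** The case for leaving the text alone has several parts.

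- **SAEs.** A reader might infer that SAEs in the gap are lost. The documents do not support that. Section 7.7 requires SAEs of any causality with onset within 30 days of dosing to be reported within 24 hours of knowledge, and the call does not end that duty. Late COVID-19 worsening that leads to hospital admission is an SAE under Section 7.6. Related AEs also stay open after the call under Section 7.5. What remains is non-serious AEs judged unrelated, and the fact that no scheduled AE assessment after the call would prompt reports of SAEs.
- **Other contacts.** It would be wrong to call this the only contact after Day 8. Follow-up samples are also due 30 ± 7 days after discharge (footnote s, Section 5.7), possibly on a different day from the call. Patients discharged before Day 6 give a sample between Days 6 and 10. Neither contact is designated as an AE assessment, so neither guarantees collection to Day 31.
- **Reading of Section 7.5.** Its closing sentence could be read as applying only once both the 30-day period and the call have passed. That reading is possible, but the sentence names only the call, so the text needs to be reconciled either way.
- **Rarity.** The gap needs both a departure from the Day 8 stay, which patients must agree to at entry (inclusion criterion 3), and a call early in the window. This stands.
- **Late days.** Drug-related AEs are expected 1 to 5 days after dosing (Section 5.3.2.1), and daily calls cover early leavers to Day 8. This stands too: the DLT period is not affected.

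**Conclusion.** The mismatch is real and limited. For discharge on Day d before Day 8, a compliant call can come up to 8-d days before the AE period ends, and the events exposed are non-serious AEs judged unrelated. There is no shortfall at the nominal call time or for patients who stay to Day 8.

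This rests on counting the period to Day 31 and on reading Section 7.5 as closing capture at the call. The number of early discharges is not stated and may be small. A reader might infer that the comparison between arms is biased. The documents give no discharge rate by arm, and the analyses are descriptive, so they support only unequal observation between patients, with an unknown split between arms.

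Small groups are the reason to care about even one event. With 5 bempegaldesleukin patients per cohort, one patient with a missed event changes a dose-level percentage by 1/5 = 20 points. In a pooled placebo group of 15 (three cohorts of 5), it changes the percentage by 1/15 = 6.7 points. The point does not threaten the trial, but the correction is cheap and worth making.

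**What to change.** In footnote r of Protocol Section 1.2 and in Section 5.7, after the call timing, add: *and in no case before Day 31 (30 days after study drug administration)*. Leave the rest of the window as it stands. The shortfall becomes 0 for every discharge day.

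The cost is one clause in two places, with no added call, visit or sample. The downside is a narrower call window for early leavers: Days 31 to 39 (9 dates) instead of Days 25 to 39 (15 dates) for discharge on Day 2, and Days 31 to 44 (14 dates) for discharge on Day 7. From discharge on Day 8 onwards nothing changes. The sample window in footnote s can stay as written, because it still overlaps the narrowed call window. SAP Section 11.2 needs no change.

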2.0 INTRODUCTION

2.1 Background

2.1.1 COVID-19

Following the outbreak of severe acute respiratory syndrome (SARS) in 2002, human coronaviruses have been reported as pathogens that cause severe symptoms in respiratory tract infections. A human coronavirus isolated from the respiratory epithelium of unexplained pneumonia patients in Wuhan, China in December 2019, initially named "2019 novel coronavirus" (2019-nCoV) and later designated "severe acute respiratory syndrome coronavirus 2" (SARS-CoV-2), causes acute lung symptoms, leading to a condition that has been named "coronavirus disease 2019" (COVID-19) (Xu 2020).

2.1.1.1 Clinical Presentation of Patients with Mild COVID-19

COVID-19 shows similarities with SARS-CoV and Middle East respiratory syndrome coronavirus (MERS-CoV) infections (Gralinski 2020). Most cases of COVID-19 reported to date are of mild severity. In China, up to 81% of patients were reported to have mild disease, however, this estimate includes a range of disease severity from asymptomatic to mild pneumonia (Wu 2020). Among the COVID-19 cases reported to the Centers for Disease and Control (CDC) from January 22 to May 30, 2020, 14% of patients were hospitalized, 2% were admitted to an intensive care unit, and 5% died. Excluding the 4% of patients who were asymptomatic, approximately 75% of patients in the US would be expected to have mild disease (Stokes 2020). Symptoms of mild COVID-19 include fever, cough, sore throat, malaise, headache, muscle pain, and gastrointestinal symptoms, without shortness of breath or dyspnea (FDA 2020). The clinical course may rapidly progress for some patients with mild COVID-19, especially for patients with risk factors for severe disease (CDC 2020a; Guan 2020; Huang 2020). Worsening of patient clinical status has been observed approximately 5 to 8 days after the onset of COVID-19 symptoms (Kujawski 2020; Huang 2020; Guan 2020; Kim 2020). In severe cases of COVID-19, the disease can cause pneumonia, severe acute respiratory syndrome, multi-organ failure, and death (FDA 2020).

2.1.2 Bempegaldesleukin (NKTR-214) for Patients who have Mild COVID-19

Bempegaldesleukin (NKTR-214) is an engineered interleukin-2 (IL-2) cytokine prodrug that provides a controlled and sustained IL-2 signal to T cells and natural killer cells. Upon administration to patients with cancer, we observed increased number and proliferation of T cells and natural killer cells (see Section 2.1.3.1), and concurrent increases in cytolytic effector molecules such as granzyme B in tumor (Bentebibel 2019). To overcome a COVID-19 infection, an innate and most importantly adaptive (T cell-mediated) immune response to the virus is required, which has been observed in surviving patients (Tan 2020a; Zheng 2020; Zhou 2020; Ma 2020 [preprint]). Lymphopenia has been identified as biomarker of COVID-19 disease severity (Richardson 2020; Tan 2020a; Ruan 2020; Zhou 2020; Yang 2020a; Thevarajan 2020; Chen 2020; Wang 2020). We are conducting this Phase 1b study to evaluate if

bempegaldesleukin can be administered safety to patients with mild COVID-19 to maintain normal or increase lymphocytes. The ultimate long-term goal of the development program is to determine if bempegaldesleukin can overcome lymphopenia in patients hospitalized for COVID-19 by correcting both the numerical and functional impairment of lymphocytes to improve survival.

2.1.3 Bempegaldesleukin (NKTR-214) Polymer Conjugation Design

Bempegaldesleukin was designed to mitigate the severe toxicities associated with administration of IL-2 (aldesleukin, Proleukin[®]). While aldesleukin is a well-established cytokine therapy first approved by the United States Food and Drug Administration (FDA) in 1992 for the treatment of metastatic renal cell carcinoma (RCC) and subsequently for the treatment of metastatic melanoma, aldesleukin has multiple shortcomings. These challenges include rapid clearance (> 95% clearance within 30 minutes), which necessitates frequent administration of high doses and resultant increased severe toxicity that led the FDA to issue a black-boxed warning (Proleukin 2018). The warning alerts clinicians and patients that aldesleukin administration has been associated with capillary leak syndrome, which may result in hypotension and reduced organ perfusion that may be severe and can result in death.

The goal of engineering bempegaldesleukin as a pegylated form of IL-2 was to reduce the treatment-limiting toxicities of aldesleukin, prolong the half-life, and ultimately enhance efficacy. The differences between aldesleukin and bempegaldesleukin are presented in Table 2.

Parameter	Aldesleukin (Proleukin) ^a	Bempegaldesleukin	
Structure	Human recombinant IL-2.	Pegylated human recombinant IL-2.	
Dosing	IV infusion every 8 hours for 5 consecutive days.	IV infusion every 2-3 weeks.	
Administration	Hospital setting. An intensive care facility and specialists skilled in cardiopulmonary or intensive care medicine must be available.	Outpatient setting ^b .	
Half-life	85 minutes	20 hours	
Primary life-threatening AEs requiring hospital monitoring	 Capillary leak syndrome. Cardiac arrhythmias (supraventricular and ventricular), angina, myocardial infarction, respiratory insufficiency requiring intubation, gastrointestinal bleeding or infarction, renal insufficiency, edema, and mental status changes. 	Primary life-threatening toxicities associated with aldesleukin have not been observed.	
	• Impaired neutrophil function and with an increased risk of disseminated infection, including sepsis and bacterial endocarditis.		

 Table 2:
 Comparison of Aldesleukin to Bempegaldesleukin

a. Proleukin 2018.

b. Bempegaldesleukin is administered in an outpatient setting when used as an immuno-oncology agent, as safety and tolerability have been evaluated in patients with advanced cancers. However, hospitalization or admission to an in-patient facility through Day 8 is required in Study 20-214-34 because safety and tolerability have not yet been evaluated in patients with COVID-19 (see Section 2.2.3).

[figure not shown]
To date, bempegaldesleukin has been studied as an immunotherapeutic agent in different oncology indications in > 600 patients with a well-tolerated safety profile that allows for outpatient administration of the compound. The majority of AEs observed have been mild to moderate in severity, transient and typically resolve in 2-4 days following study drug administration. Bempegaldesleukin has been routinely administered to cancer patients at 0.006 mg/kg and nivolumab 360 mg q3w. In Study 20-214-34, a single dose of bempegaldesleukin will be administered to adults with mild COVID-19 at a starting dose of 0.00075 mg/kg; this starting dose is one-eighth of the 0.006 mg/kg dose that is commonly used in the oncology setting in combination with other agents and is one-twelfth of the maximum tolerated dose (MTD) for monotherapy (ie, 0.009 mg/kg; see Section 2.1.4.2.1) in late stage cancer.

